#### 4. STUDY ENDPOINTS

## 4.1. PRIMARY ENDPOINTS

Safety: The main objective is the evaluation of the overall safety of RZL-012 injection into the subcutaneous fat. Therefore, the primary endpoint will be the incidence of intolerable side effects and all adverse events of RZL-012 injection into the subcutaneous fat. The dose escalation scheme will be stopped if at any dose cohort, 2 patients will experience intolerable side effects.

Efficacy: The primary endpoint for efficacy is a significant thermogenesis at the injected site compared with the contra-lateral, non-injected site. This was monitored by sensitive ( $\pm$  0.1 °C) Infra-Red thermal camera. A thermogenic effect is defined by an increase of 1 °C in the injected site when compared to the surroundings and/or the non-injected site, apparent at least 28 days after injection and non-related to inflammatory response as determined by inflammatory cytokines. The primary efficacy evaluation will be supported by results from secondary endpoints, including MRI, biopsy and biomarkers.

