## 6.1.8.4. Inflammatory Markers and Cytokines

Testing of inflammatory markers and cytokines values from the 2nd, 3rd and 4th cohorts (on RZL-012 treated and placebo treated subjects in each cohort) will be conducted in order to explore the mode of action at clinic admission visit (Day -1)to establish baseline values (4 mL

blood per subject). Additional cytokines testing will be conducted study visits Day 7, 14, 21 and 28.

Inflammatory and cytokines will include: CRP, Adiponectin, CD-163, Interleukin [IL]-1β, IL-4, IL-6, IL-10, IL12p70, IL-13, IL-23, Tumor necrosis factor [TNF] α, and TGFβ1.

Inflammatory and cytokines level will be measured by multiplexed ELISA kits, called Q-PlexTM. Q-Plex Arrays are able to measure the concentration of multiple proteins in each sample and to quantify cytokines levels. Blood samples (4 mL) will be centrifuged at 1200 G in 4  $^{0}$ C for 10 minutes, plasma collected in aliquots (minimum of 2 aliquots of 500  $\mu$ L each) within 20 minutes of centrifugation and flash frozen on dry ice. Processed samples will be frozen in -80  $^{0}$ C. Plasma aliquots will be analyzed by Quansys Biosciences.

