## 6.1.17.2.6. Inflammatory Markers and Cytokines Changes

To determine drug mechanism of action, inflammatory markers and cytokines level in cohorts 2 through 4 will be evaluated by comparing to baseline. Inflammatory markers and cytokines changes definition is an apparent change from baseline.

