## 6.2.5. Subject Site Visits

Subject site visits will be performed  $\pm$  1 days from scheduled date for study visits Day 0-28 and  $2\pm$  1 days from schedule date for follow-up visits (Day 56-168). All data relevant for the visit needs to be obtained within 3 days (e.g., blood tests) of visit.

Subject sites visits will include procedures as described in Appendix I - Trial Schedule of Events.

For site visit that results in study discontinuation, see termination visit in Section 6.2.6.

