### 10.5.2. Subject Disposition

A detailed description of subject accountability including count of subjects included, randomized, exposed, completed (i.e., subjects who complete the study treatment) and discontinued along with the main reason for discontinuation will be generated for each cohort and for all subjects. All withdrawals from the study, taking place on or after study drug injection, will be fully documented in the body of the Clinical Study Report.

Note that the actual study duration is for a period of maximum 6 months, with efficacy analyses being conducted at 28 days and 56 days for all dose levels and up to 6 months for the 3rd and 4th cohorts or for the highest dose level achieved.

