## 5.3 Study Objectives and Endpoints

- 5.3.1 Primary Objectives:
- 5.3.2 Evaluation of the overall safety and preliminary efficacy of RZL-012 after injection into the subcutaneous fat.
- 5.3.3 Primary Endpoints

- 5.3.4 Safety: The main objective is the evaluation of the overall safety of RZL-012 injection into the subcutaneous fat. Therefore, the primary endpoint will be the incidence of intolerable side effects and all adverse events of RZL-012 injection into the subcutaneous fat. The dose escalation scheme will be stopped if at any dose cohort, 2 patients will experience intolerable side effects.
- 5.3.5 Efficacy: The primary endpoint for efficacy is a significant thermogenesis at the injected site compared with the contra-lateral, non-injected site. This was monitored by sensitive (± 0.1 °C) Infra-Red thermal camera. A thermogenic effect is defined by an increase of 1 °C in the injected site when compared to the surroundings and/or the non-injected site, apparent at least 28 days after injection and non-related to inflammatory response as determined by inflammatory cytokines. The primary efficacy evaluation will be supported by results from secondary endpoints, including MRI, biopsy and biomarkers
- 5.3.6 Secondary Objectives:
- 5.3.7 Determination of RZL-012 pharmacodynamics and pharmacokinetics. Evaluation of the existence of a thermogenic effect and the extent, duration and tissue associated changes of the thermogenic response to RZL-012, via minimal invasive means (injected-site thermogenesis imaging, Magnetic Resonance Imaging (MRI) and biopsy) after subcutaneous injection into fatty tissue below the skin.
- 5.3.8 Secondary Endpoints
- 5.3.9 Duration of the thermogenic effect, defined as a net-delta  $\geq 1$
- 5.3.10 Local reduction in fat mass as determined by MRI.
- 5.3.11 Clinical laboratory changes from baseline including improvement in fasting blood glucose and lipid profile.
- 5.3.12 Establishing pharmacokinetic profile for RZL-012.
- 5.3.13 Anthropometric changes from baseline, including body weight change.
- 5.3.14 Elucidation of the histological changes account for the thermogenic effect by biopsy of the injection site.
- 5.3.15 Change from baseline in inflammatory markers and cytokines.
- 5.4 Overall study design and plan

Medi Stat Statistics in Medicine	DOCUMENT NUMBER: 050-BST-PLN-001	PAGE: 14 of 31
TITLE: Statistical Analysis Plan		EFFECTIVE DATE: 14/Nov/2018 REVISION NUMBER: 2.0

- 5.4.1 Study Design

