## 5.8 Statistical Analysis

- 5.8.1 General
- 5.8.2 All measured variables and derived parameters will be listed individually and, if appropriate, tabulated by descriptive statistics. For categorical variables summary tables will be provided giving sample size, absolute and relative frequency. For continuous variables summary tables will be provided giving sample size, arithmetic mean, standard deviation, standard error, coefficient of variation (CV%), median, minimum and maximum of variables, and 95% confidence intervals of means.
- 5.8.3 The data is analyzed using the SAS ® version 9.3 or higher (SAS Institute, Cary North Carolina). Analyses presented in the clinical report but not mentioned in the SAP are unplanned or ad-hoc analyses.
- 5.8.4 Statistical methods presented in the SAP may be slightly different from those that are presented in the protocol. Differences are clearly stated and the SAP supersedes the protocol only with regard to the way data will be handled and analysed.
- 5.8.5 Derived Data
- 5.8.6 Definition of baseline
- 5.8.7 Baseline is defined as the last non-missing value prior to the patient start of treatment (screening or baseline visit).
- 5.8.8 End of Study
- 5.8.9 The end-of-study visit is defined as Day 168.
- 5.8.10 Disposition of subjects (Table 14.1-1 14.1.2)
- 5.8.11 The number of subjects that are randomized into the study, the number of subjects in the Safety, efficacy analysis set, and PK populations, and the number of study completers will be presented.
- 5.8.12 The reasons for early termination/ withdrawal will be summarized.

- 5.8.13 Demographic and Baseline data (Tables 14.1-3-14.1-4)
- 5.8.14 Baseline and demographic data will be summarized in appropriate tables using the Safety population. The data includes demographic characteristics (age and gender) and medical history.
- 5.8.15 Efficacy Analysis
- 5.8.1 The primary endpoint for efficacy is a significant thermogenesis at the injected site compared with the contra-lateral, non-injected site.
- 5.8.2 The average temperature will be presented in a tabular form by visit, side (treated / not treated) and treatment received (RZL-012 / placebo) by cohort and overall. Difference between the sides (treated not treated) will be presented in a tabular form by visit treatment along with the change from baseline (net-delta) in these differences by cohort and overall.

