- 5.8.3 Kruskal-Wallis will be used to compare the net-delta between the study arms for the relevant cohorts and visits.
- 5.8.4 The number and percent of subjects with a thermogenic effect, defined as a net-delta ≥ 1, will be presented by cohort and visit for the subjects in the active arm. The duration of the thermogenic effect after the Day 28 visit, for subjects in the active arm with thermogenic effect at the Day 28 visit will be presented.
- 5.8.5 Subcutaneous Fat Mass (SFM) ratio (treated sites / control sites) averaged over the MRI slices will be presented in tabular form by visit, treatment and cohort. The change from baseline in this ratio (in % from the ratio at baseline) will be presented in the same manner, and compared between the treatment arms with Kruskal-Wallis test.
- 5.8.6 Changes from baseline in fasting blood glucose, lipid profile, anthropometric changes, inflammatory markers and cytokines will be presented by visit, treatment, and cohort.
- 5.8.7 Histology results will be presented in tabular form by treatment for relevant subjects.
- 5.8.8 Safety analysis
- 5.8.9 Safety data will be summarized for the Safety population.
- 5.8.10 Adverse events will be coded according to coding dictionaries (the most updated version of MedDRA) and presented in tables by System Organ Class (SOC) and Preferred Term (PT) and by treatment group.

- 5.8.11 The incidence of AEs, as well as the intensity and relationship to study drug will be summarized by treatment group.
- 5.8.12 The incidence of all adverse events will be presented by treatment overall and by cohort along with two sided 95% exact binomial Confidence Interval (CI).
- 5.8.13 The incidence of intolerable side effects will be presented by treatment overall and by cohort along with two sided 95% exact binomial Confidence Interval (CI).
- 5.8.14 Concomitant medication verbatim terms (as recorded on the CRFs) will be coded to Anatomical Therapeutic Chemical (ATC) Level 2 and 4 using the World Health Organization (WHO) dictionary.
- 5.8.15 Interim Analysis
- 5.8.16 An interim analysis is planned at the end of each cohort for evaluation of efficacy. For this purpose, a data lock (except for externally collected data such as PK) will be implemented after each cohort is completed. Upon lack of trends in efficacy due to effect size, the Sponsor will consider study termination

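### The stated primary thermogenic-effect rule differs from the net-delta rule that is analysed; no responder visit is named primary, and responders are counted in the active arm only

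*Protocol*

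**What the plan says.** **Endpoint text.** The Protocol synopsis, Protocol 4.1 and 10.2.2, and SAP 5.3.5 give the same definition. Protocol 4.1 requires the injected site to be 1 °C warmer than its comparator and the effect to be "apparent at least 28 days after injection and non-related to inflammatory response as determined by inflammatory cytokines". SAP 5.3.5 words the comparator and timing as "when compared to the surroundings and/or the non-injected site, apparent at least 28 days after injection". No baseline term appears in the definition.

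**Operational text.** Protocol 6.1.17.1.2, under the evaluation of primary endpoints, uses a 1 °C increase from baseline in the treated minus untreated difference (net delta), apparent *by* 28 days, with no cytokine condition. Protocol 10.5.5 and the Efficacy Analysis part of SAP 5.8 count subjects with net-delta of at least 1. That count "will be presented by cohort and visit for the subjects in the active arm". The same SAP part opens by restating the endpoint against one comparator only: "The primary endpoint for efficacy is a significant thermogenesis at the injected site compared with the contra-lateral, non-injected site".

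**Visits.** Protocol 10.5.2 describes "efficacy analyses being conducted at 28 days and 56 days for all dose levels", continuing up to 6 months at the highest doses. It calls no visit primary. The duration summary is conditioned on an effect at the Day 28 visit.

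**Cytokines.** Protocol 6.1.8.4 and Table 2 limit sampling to cohorts 2 to 4. After the Day -1 baseline, "Additional cytokines testing will be conducted study visits Day 7, 14, 21 and 28". Protocol 6.1.17.2.6 gives the only criterion: "Inflammatory markers and cytokines changes definition is an apparent change from baseline".

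**The concern.** Two definitions of the primary efficacy response stand side by side inside each document, and neither document says which one governs the reported result. They differ in comparator, baseline adjustment, timing and the inflammatory exclusion, so they can classify the same subject differently.

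The stated aim in Protocol 10.1 is to find the tolerated dose with the largest thermogenic effect, and Protocol 10.7 plans an efficacy look after each cohort that may lead the sponsor to consider termination. Neither section says that the responder rule drives these decisions, but a reader would expect the primary definition to be fixed before the looks begin.

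Counting responders only among active subjects also leaves the 1 °C rate without a summarised vehicle rate to set it against.

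**Working it through.** **1. The plan's own figures.** Four cohorts of 6 active and 2 placebo: 4 × (6 + 2) = 32; active 4 × 6 = 24; placebo 4 × 2 = 8. These match Protocol 10.3. No power, effect size or SD is given, so there is no power figure to check.

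**2. Clause by clause.**

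| Element | Endpoint text (Protocol 4.1, 10.2.2; SAP 5.3.5) | Protocol 6.1.17.1.2 | Responder table (Protocol 10.5.5; SAP 5.8) |
|---|---|---|---|
| Threshold | 1 °C | 1 °C | 1 °C |
| Comparator | surroundings and/or untreated side | untreated side | untreated side |
| Baseline term | none stated | yes | yes |
| Timing | at least 28 days | by 28 days | every visit |
| Cytokines | required non-inflammatory | none | none |
| Arms | not restricted | not restricted | active only |

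A rise seen at Day 14 or 21 and gone by Day 28 would meet 6.1.17.1.2 and appear in the responder table at those visits, yet fail the endpoint text. Timing is a live question: Protocol 1.2.4 reports that the phase 0 rise was mostly evident at Day 14 or 21 in the highest-dose cohort. It does not say how many had lost the rise by Day 28.

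**3. Where the table reports an effect.** From Protocol 6.1.12 and Table 2, post-dose imaging is on Days 1, 7, 14, 21, 28 and 56 in all cohorts, and on Days 84, 112, 140 and 168 as well in cohorts 3 and 4. Cohort-by-visit cells: 2 × 6 + 2 × 10 = 32. Cells before Day 28: 4 cohorts × 4 visits = 16, which the endpoint text would exclude.

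**4. Whether the cytokine condition can be assessed.** At the two visits analysed for all doses there are 24 × 2 = 48 planned active subject-visits.

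- Same-visit samples required: 3 cohorts × 6 subjects × 1 visit (Day 28) = 18, and 18/48 = 37.5%. Day 56 contributes none.
- Draws up to Day 28 also allowed to inform Day 56: cohorts 2 to 4 give 18 × 2 = 36, and 36/48 = 75%. Cohort 1 still contributes none of its 6 × 2 = 12.

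Even where samples exist, no rule says which of the 12 markers, or how large a change, counts as inflammatory.

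**5. What a placebo column could show.** With no responders among n, the exact two-sided 95% upper limit is 1 − 0.025^(1/n).

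- Pooled placebo, n = 8: 1 − 0.025^(1/8) = 36.9%.
- One cohort, n = 2: 1 − 0.025^(1/2) = 84.2%.

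The 8 is a planned maximum. Under Protocol 5.4 a single withdrawal in cohort 1 or 2 is not replaced, and nothing is imputed.

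**The case against.** The best defence is that the calculation is not open. Net-delta of at least 1 °C is prespecified in both documents and agrees with Protocol 6.1.17.1.2. The SAP is to be signed before hard lock and takes precedence on analysis. The by-visit table will contain a Day 28 row, and the duration summary already starts from that visit. All of this stands. A reader might infer that the primary rule will be chosen after the data are seen, and the documents do not support that. What remains open is which definition is called primary, which visit is the headline, and what cytokines do.

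Other strong readings also fail:

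- *The SAP departs silently from the protocol.* It repeats both rules, so it carries the inconsistency over. The SAP cites protocol V1.4, whereas the supplied protocol is 001.2, so whether the wording *by 28 days* survives cannot be checked. The conflict within the SAP does not depend on this.
- *Placebo is left out of efficacy.* Continuous net-delta is tabulated and tested between arms, and individual thermogenesis results are listed. Only the responder and duration summaries are limited to the active arm.
- *Most responder classifications would change.* The 18 of 48 counts where the cytokine condition could be assessed, under a same-visit assumption that the plan does not state. No changed classification is shown.
- *Error control is damaged.* Protocol 10.5.1 describes mainly descriptive analyses with nominal p-values.
- *Day 28 satisfies every wording.* Protocol 6.1.17.2.1 defines a sustained effect as evident after 28 days, which is a separate secondary concept.

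It is also fair to say that a per-cohort placebo rate will be very imprecise.

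**Conclusion.** The point holds as a mismatch of definitions that should be fixed. The stated primary rule is not the one analysed. Its cytokine condition cannot be carried out in cohort 1 under any reading, has no same-visit sample after Day 28, and has no criterion anywhere. It is assessable in at most 18 of 48 planned active subject-visits at Days 28 and 56 if same-visit samples are required. That figure assumes full enrolment and attendance.

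No visit is primary for the responder count, and the 1 °C rate has no summarised vehicle reference. Different classification under the two rules is possible, not shown. The consequence is an ambiguous reading of the primary efficacy result in a mainly descriptive study. Confidence is high for the textual conflict and lower for how much it would change the reported result.

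**What to change.** 1. **One definition.** In the Protocol synopsis, 4.1 and 10.2.2, and in SAP 5.3.5, replace the comparator and timing wording with the rule the analysis already uses: change from baseline of at least 1 °C in treated minus contralateral temperature. Name the scheduled Day 28 visit as the primary responder visit, including its window of plus or minus "1 days from scheduled date for study visits Day 0-28". Carry the same visit into Protocol 6.1.17.1.2 and 10.5.5 and the SAP Efficacy Analysis. Keep other visits as secondary, and leave the sustained effect in 6.1.17.2.1 as its own secondary endpoint.
2. **Cytokines.** State that the condition is not evaluable in cohort 1, nor by same-visit sampling after Day 28. The sponsor then chooses: report cytokines as supportive data for cohorts 2 to 4, or keep the condition and fix markers and thresholds before unblinded data are reviewed.
3. **Placebo responders.** Tabulate them beside active, by cohort and with placebo pooled, with exact 95% intervals and a note on imprecision.
4. **Record the timing.** Data are locked after each cohort, so date the change and state which cohorts had already been reviewed.

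A separate matter must be reconciled by the sponsor. Footnote f of the schedule of events in both documents says that the cohort 4 dose is divided into two clusters two weeks apart, while Protocol 3.3.1 and 6.2.3.1 describe a single treatment.

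The cost is an amendment to the endpoint wording in both documents and one table column from images already scheduled. The price is that a rise which fades before Day 28 is not a primary response, and that the placebo rate rests on at most 8 subjects.

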# 4.2. SECONDARY ENDPOINTS

Following are the study's secondary endpoints:

- 1. Duration of the thermogenic effect, defined as a net-delta ≥ 1, see definition in Section 6.1.17.2.1.
- 2. Local reduction in fat mass as determined by MRI, see definition in Section 6.1.17.2.2.
- 3. Clinical laboratory changes from baseline including improvement in fasting blood glucose and lipid profile, see definition in Section 6.1.17.2.3.
- 4. Establishing pharmacokinetic profile for RZL-012, see definition in Section 6.1.15.

- 5. Anthropometric changes from baseline, including body weight change, see definition in Section 6.1.17.2.4.
- 6. Elucidation of the histological changes account for the thermogenic effect by biopsy of the injection site, see definition in Section 6.1.17.2.5.
- 7. Change from baseline in inflammatory markers and cytokines, see definition in Section 6.1.17.2.6.

# 5. STUDY POPULATION

#### 5.1. INCLUSION CRITERIA

Subjects meeting all of the following criteria will be eligible for study participation:

- 1. Adult male subjects 20-60 years old.
- 2. Subject is considered overweight and obese, with  $27.5 < \text{Body Mass Index (BMI)} \le 34.9$ .
- 3. Significant subcutaneous abdominal fat as defined by WHR  $\geq$  0.9.
- 4. Subjects with stable weight in the last 3 months by medical history.
- 5. Not one of the following eating disorders by subject's declaration: anorexia nervosa, bulimia nervosa.
- 6. Generally considered healthy according to medical history, physical examination, ECG and laboratory evaluation with a special emphasis on metabolic parameters (fasting glucose concentration < 100 mg, normal blood pressure).
- 7. Subject is willing to refrain from sexual activity or agrees to use a double-barrier contraceptive device (e.g., condom and spermicide) for 4 weeks after treatment with RZL-012.
- 8. Subjects must be able to adhere to the visit schedule and protocol requirements and be available to complete the study.
- 9. Subjects must sign an informed consent indicating that they are aware of the investigational nature of the study.

# 5.2. EXCLUSION CRITERIA

Subjects meeting any of the following criteria will be excluded:

- 1. Subjects weighing less than 75 kg.
- 2. Subjects who have reduced/gained weight more than 5 % of their current body weight in the last 3 months.
- 3. Unable to tolerate subcutaneous injection.

- 4. Subjects with uncontrolled cardiac, hepatic, renal or neurologic/psychiatric disorders, that in the opinion of the investigator put the subject at significant risk, are not eligible.
- 5. Subjects who test positive to Hepatitis B virus (HBV), Hepatitis C virus (HCV), or Human immunodeficiency virus (HIV) are not eligible.
- 6. Subjects with a clinical history of primary or secondary immunodeficiency, autoimmune disease or subjects taking immunosuppressive drugs such as corticosteroids are ineligible.
- 7. As a result of medical review, physical examination, the Principal Investigator (PI) (or medically qualified nominee) considers the subject unfit for the study.
- 8. Medication use on regular basis including blood and blood products.
- 9. Positive drug and alcohol tests.
- 10. Known sensitivity to components of the injection formulation.
- 11. Prior wound, tattoo or infection in the treated area.
- 12. Excessive growth of hair in the abdomen region.
- 13. Claustrophobia or MRI incompatible device or implant.

# 5.3. SUBJECT IDENTIFICATION

A unique code numbers will be assigned by the investigator to the trial subject rather than the subjects' names, personal identification numbers, and/or addresses to protect the subject's identity. The code numbers and initials will be used in lieu of the subject's name when the investigator reports adverse events and/or other trial related data.

